We will take great care in the informed consent process of all participants. To ensure that the participants understand what is being requested and the implications of participation, the impact of an elevated amyloid PET scan will be discussed at great length during the consenting process. We will review the consent forms with the participants and they will be allowed to ask for clarification or questions at any point.

Consent of participants will be a requirement for participation in the research. Participants will have normal cognition and will have capacity to provide consent. No surrogates will be used.

At the beginning of the second in-person appointment, the study partner will be consented to participate in his/her specific responsibilities, specifically participating in the CDR scale in Visit #2. The study partner's consent form will include language for him/her to be re-contacted by the study coordinators to collect additional information from the study partner's perspective.

Should the participant want his/her study partner present at any visit, and the study partner is unable to accompany him/her, then a substitute study partner (a family member or a paid caregiver) can be sent.

V. Study Procedures

This clinical trial will randomize 370 cognitively normal participants enriched for their odds of having elevated amyloid by age, family history and *APOE* genotype. Written informed consent for the study will be sought from all participants. The site-PI or appropriate study staff at each site will obtain written consent through a standard informed consent document approved by their site's Institutional Review Board. Informed consent processes are detailed in "Subject Enrollment" above. Participants who pass screening will undergo amyloid imaging and then be randomized to either (1) learn the results of their amyloid scans at the fourth visit, or (2) not learn their result at the fourth visit, though will receive a delayed scan result disclosure within approximately four weeks after their 6-month follow-up visit. All participants will receive an AD Dementia Risk Assessment based on individual risk factors including age, gender, family history and race/ethnicity, with intervention arm participants additionally receiving their amyloid imaging results. Follow-up after disclosure will occur via a phone call and up to three in-person

visits.

Step 1 – Recruitment:

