Step 8 – Visit #4: Alzheimer's Disease Dementia Risk Disclosure with (D+)/without (D-) Amyloid Scan results (in-person)

All participants will return to the study site for their fourth in-person visit to receive their Alzheimer's Disease Dementia Risk Assessment either with or without their amyloid imaging result, as determined by random assignment. At each site, a trained disclosure provider will present the participant with generalized reference curves of Alzheimer's disease risk based on age, gender, family history, and race/ethnicity. If the participant is randomized to receive their amyloid imaging result, the disclosure provider will communicate whether they have elevated or not elevated amyloid and present his/her AD dementia risk estimate compared to the general population.

If the participant is randomized to not receive their amyloid imaging result at this visit, but will receive their scan result at the end of the study, the disclosure provider will only present the participant's AD dementia risk estimate based on age, gender, family history, and race/ethnicity.

The participant will have the opportunity to ask questions.

Step 9 – Phone Call #4: 1-3 Day Safety Check

The study coordinator will call the participant in 1-3 days to assess the participant's status as a safety check to assess any psychological impact of the disclosure visit, regardless if they are in the immediate scan disclosure group or delayed scan disclosure group.

Psychological impact of the disclosure visit will be measured by using the Impact of NeuroImaging for Alzheimer's Disease (INI-AD) scale adapted to this study to measure the impact of amyloid imaging for AD⁵³ and using the intrusion subscale of the Impact of Event Scale (IES). The INI-AD scale is a 16-item multi-dimensional assessment of risk disclosure across distress, uncertainty, and positive experience.

The INI-AD was developed and validated in our prior REVEAL trials, and will be adapted for this safety check by phone to allow for differentiation of the emotional effects of risk disclosure from more general distress or worry.

The IES-intrusion subscale, a 7-item self-reported measure,⁵⁴ assesses response related to a specific stressful life event, and has been specifically anchored to test-related distress in studies of the impact of health risk information, including all previous REVEAL Study trials.

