Pre-specified cut-off scores of safety screening measures are listed under the "Safety of Participants" section below. Those found to be cognitively or emotionally impaired will be offered appropriate referral. Should safety be a concern, the disclosure provider or study coordinator will schedule additional in-person visits or phone calls as needed or make a referral to a mental health professional as indicated.

Step 10— Visit #5: 6-Week Follow-Up + Neuropsychological test battery + Secondary Outcome Measures + Cognitive Measures + Health Behavior Surveys

Participants will return in-person six weeks (Visit 5) post-disclosure. The neuropsychological battery, consisting of the 1) ADCS-PACC as our primary outcome measure to assess neuropsychological status,⁴⁴ 2) TOMM,⁵⁵ 3) Digit span forward test⁴⁶ TOPF⁴⁷ will be administered.

The secondary outcomes measures at six weeks will measure anxiety and depression with the GDS,⁴⁰ mini-STAI,⁴¹ and CSSRS measures⁴²; test-specific distress with the Impact of Events Scale (IES)⁵⁴; psychological impact of risk disclosure with the adapted INI-AD; quality of life with the SF-12 measure⁵¹; and perceived time with the Future Time Perspective scale.⁵²

Subjective cognitive measures of the Metamemory in Adulthood (MIA),⁴⁹ Memory Function Questionnaire (MFQ),⁵⁰ and Cognitive Function Instrument (CFI)⁵⁶ will be administered.

Participants will also take the follow-up health behavior surveys to determine the type and frequency of behavior changes in response to learning risk information. Information

collected will include assessing health behavior changes, advanced planning, insurance changes (i.e. purchasing or altering long-term care policies), medication changes, willingness to enroll in clinical research, stigma, and tolerance of research risk.

In addition, Dynamic Experiments for Estimating Preference (DEEP)⁶¹ behavioral assessments will measure participant risk and time preference as presented electronically through various decision-making scenarios.

Step 11 – Visit #6: 6-Month Follow-Up + Neuropsychological test battery + Secondary Outcome Measures + Cognitive Measures + Health Behavior Surveys + Additional Stereotype Threat Measures

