The secondary outcomes measures at six months will measure anxiety and depression

with the GDS,⁴⁰ mini-STAI,⁴¹ and CSSRS measures⁴²; test-specific distress with the Impact of Events Scale (IES)⁵⁴; psychological impact of risk disclosure with the adapted INI-AD; quality of life with the SF-12 measure⁵¹; perceived time with the Future Time Perspective scale⁵², Essentialist Beliefs about Aging Question⁶³, and a question about feelings of stereotype threat about Alzheimer's disease risk..

Subjective cognitive measures of the Metamemory in Adulthood (MIA),⁴⁹ Memory Function Questionnaire (MFQ),⁵⁰ and Cognitive Function Instrument (CFI)⁵⁶ will be administered.

Participants will also take the follow-up health behavior surveys to determine the type and frequency of behavior changes in response to learning risk information. Information collected will include assessing health behavior changes, advanced planning, insurance changes (i.e. purchasing or altering long-term care policies), medication changes, willingness to enroll in clinical research, stigma, and tolerance of research risk.

In addition, Dynamic Experiments for Estimating Preference (DEEP)⁶¹ behavioral assessments will measure participant risk and time preference as presented electronically through various decision-making scenarios.

Finally, the Everyday Discrimination Scale⁶² has been developed and will be used to assess perceived discrimination at Visit 6.

Step 12 – Visit #7: Delayed Amyloid Scan Disclosure for Initial D- Group

At the end of study data collection, participants in the control arm will return in-person (Visit 7) within approximately four weeks after their 6-month follow-up to learn their amyloid imaging results.

Step 13 – Phone Call #5 for initial D- Group after delayed disclosure: 1-3 Day Safety Check

Participants initially randomized to be in the delayed non-disclosure (D-) group, who later learn their amyloid imaging scan results at Visit #7 will be called by the study coordinator in 1-3 days to assess the participant's status as a safety check. Psychological impact of the disclosure visit will be measured by using the adapted Impact of NeuroImaging for Alzheimer's Disease (INI-AD) scale.⁵³

VI. Biostatistical Analysis

Data Collection

Data will be collected by the study coordinator and project manager, and monitored by the PI. The PI will be responsible for monitoring and assuring the validity and integrity of all data and adherence to the IRB approved protocol.

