Based on this calculation, we have set a target to enroll n=50 in each of the 2 elevated amyloid groups (A+D-, A+D+). Due to a much lower than anticipated rate of amyloid positivity and a dropout rate of approximately 10%, we plan to enroll 370 total participants and achieve 100 completed 6 month visits to reach our group enrollment targets of n=50 for each elevated amyloid group.

VII. Risks and Discomforts

Psychological risks: We recognize that persons with normal cognition who learn they have elevated amyloid and an increased risk of developing AD dementia could experience psychological distress. We will monitor psychological well-being in our participants by pre-screening potential participants for anxiety and depression and administering standardized rating scales with pre-specified cut-off scores for affect and anxiety at scheduled follow-up visits after disclosure of PET amyloid imaging results. Additional monitoring and appropriate actions will be taken based on conversations between the study staff (clinician judgment) and participant.

For the 6-month visit digit-span task, we will examine how memory performance is affected by task instructions. Although the purpose of all the included cognitive measures is to assess the link between amyloid status and performance, during this task we will explicitly state this

relationship. Although we expect this to increase concerns about task performance, we do not expect this to create emotional distress. However, we will monitor responses. This will be done via conversations between the study staff (clinician judgment) and participant.

Deception: Mild deception will be used during the 6-month visit digit-span task. More specifically, during the initial trials of this task participants will be told that the purpose is to calibrate the equipment. No calibration will be conducted, but this instruction will reduce any evaluative concerns that may be felt by the participants. We do not anticipate this mild deception to create any distress. However, participants will be fully debriefed about this at the end of the study and their questions will be answered.

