Should a serious adverse event (e.g., self-inflicted physical harm due to receipt of test results, severe acute depression or anxiety attributed to receipt of test results, etc.) occur, the investigator at that site would notify the co-PIs and the multidisciplinary Data Safety and Monitoring Board via email immediately following the event. They would review the case in question and additional study data as needed to make recommendations as to how we can improve the safety of the study, or if the study needs to be halted.

Ensuring Safety of Human Subjects

In previous REVEAL Study clinical trials that have involved disclosure of AD dementia genetic risk information, we have developed the following detailed and documented procedures for reducing risks to participants that we have adapted for this study that will involve the disclosure of amyloid imaging.

In addition to careful and thorough communication with potential participants around the consent process, we have several layers of protection built into this protocol that have adequately guarded against any adverse consequences to date. These include:

- A. Pre-screening of all participants for clinically significant depression and anxiety.
- B. Careful education defining amyloid imaging and the meaning of amyloid imaging results.
- C. Scheduled follow-up visits after disclosure of PET amyloid imaging result with standardized rating scales for affect and anxiety. Additional monitoring and appropriate actions will be taken based on conversations between the study staff (clinician judgment) and participant, as well as pre-specified cut-off scores in screening measures:
 - Impact of Events Scale (IES): >25 increase monitoring
 - Geriatric Depression Scale (GDS) (range 0 to 15): >10 exclude. 6-10: Increase monitoring at investigator discretion and look at change from previous score
 - State-Trait Anxiety Inventory (STAI) (range 6-24): ≥ 19 exclude. 17-18 Increase monitoring at investigator discretion and look at change from previous score
 - Columbia Suicide Severity Rating Scale (CSSRS): Exclude any serious suicidal risk, based on investigator's judgment, can be followed up by site designated mental health professional and increase monitoring

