There is no direct benefit from participating in this study. This is not a treatment study, and participants will not receive any medication. By participating REVEAL-SCAN, participants may be eligible to participate in other research studies.

Trials that require disclosing AD biomarker results to cognitively normal older adults may present the prospect of empowering people to action beyond research participation, such as adopting healthy behaviors and lifestyle changes, but they may also cause harm to both perceived and actual cognitive performance, mood, and social and personal well-being. Prior

data from the REVEAL Study suggests that the information that subjects learn may decrease their anxiety about developing AD (or about their close friend, relative or spouse' chance of developing AD) or may allow individuals to make long-term decisions for the future.^{53,58-60}

The results of our study will be first-of-their kind data to measure whether such harms are real, and, if they are, their magnitude and severity. This knowledge will be of substantial importance to AD investigators, clinicians and healthcare policy makers, and, therefore, we believe the risks to the participants are reasonable and justified.

IX. Monitoring and Quality Assurance

The risks of the study are outlined above. The study clinician/project manager will be responsible for the monitoring of participant outcomes, under the supervision of the PI. Frequent contact with the study clinician, both by phone and in person at the designated follow-up sessions, will be our primary source of clinical participant monitoring. Participants will be contacted by phone within 1-3 days of receiving their AD risk assessment in order to check in on their emotional state and answer any questions regarding the information or the study itself. At minimum, the study clinician will also meet with each participant for in-person follow-ups 6 weeks and 6 months after receiving their risk assessment. At each of these follow-up appointments, the study clinician will also review participants' mood screening measures and other survey responses in real time in order to help look for possible adverse psychological reactions.

Additionally, at minimum, the study clinician will monitor safety through the completion of mood scales, review participants' mood screening measures and other responses in real time in order to help look for possible adverse psychological reactions.

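### The scheduled visits with affect and anxiety scales promised after PET disclosure do not exist for the delayed-disclosure (D-) arm, which gets one early call with a scale that has no stated cut-off

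*Protocol*

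**What the plan says.** Protocol Section VII makes the promise twice. Under Psychological risks, well-being is to be monitored by pre-screening and by "administering standardized rating scales with pre-specified cut-off scores for affect and anxiety at scheduled follow-up visits after disclosure of PET amyloid imaging results". Under Ensuring Safety of Human Subjects, item C lists as a layer of protection: "Scheduled follow-up visits after disclosure of PET amyloid imaging result with standardized rating scales for affect and anxiety". Item C then gives limits for the IES, GDS and STAI. The CSSRS is left to investigator judgment; a concern "can be followed up by site designated mental health professional and increase monitoring". Neither statement is limited to one arm.

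The schedule is set elsewhere. Section IX has the study clinician meet each participant, at minimum, for "in-person follow-ups 6 weeks and 6 months after receiving their risk assessment". That assessment is given at Visit #4 (Section V, Step 8). For D- it contains only an estimate from age, gender, family history and race/ethnicity. The D- scan result is given at Visit #7 (Step 12), within about four weeks after the 6-month visit. Step 13 then provides that D- participants "who later learn their amyloid imaging scan results at Visit #7 will be called by the study coordinator in 1-3 days", and the only instrument it names is the adapted INI-AD.

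**The concern.** Section VII names distress on learning of elevated amyloid as a psychological risk and offers scheduled visits with scored scales as a safeguard. A reader of that section, including an ethics committee or the DSMB, would take it to apply to everyone who receives the result. If it does not apply to D-, the protocol misdescribes its own protection for about half of the people told that they have elevated amyloid.

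Scheduled scales exist to pick up distress that the participant does not volunteer. Section IX expects non-serious adverse events to be mostly threshold exceedances on the GDS or Mini-STAI. If neither scale is scheduled after the D- result, a quiet safety record for that period says little.

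**Working it through.** **Schedule, side by side** (Protocol Section V, Steps 3, 5 and 8-13). Step 7 attaches the arm names the wrong way round, but Section II and Steps 8 and 12 make clear that D- is the delayed arm.

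| | D+ | D- |
|---|---|---|
| GDS, mini-STAI and CSSRS before the scan result | Visits #1, #2 | Visits #1, #2, #5, #6 |
| Scan result given | Visit #4 | Visit #7 |
| Call 1-3 days after the scan result | Call #4: INI-AD (16 items) and IES-intrusion (7 items) | Call #5: INI-AD (16 items) |
| Later scheduled visits with GDS, mini-STAI, CSSRS and IES | Visits #5, #6 | None |

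After the scan result, D+ has 3 scales with numeric limits (IES, GDS, mini-STAI) x 2 visits = 6 administrations, plus 2 of the CSSRS. D- has 0.

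The overview in Section V does not add a visit for D-. It says "Follow-up after disclosure will occur via a phone call and up to three in-person" visits, and for D- those are Visits #5, #6 and #7. Visit #7 is the disclosure itself, and Step 12 lists no scale for it.

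No INI-AD cut-off appears in Section III, in item C or in Section IX. Step 9 (Call #4) points to the cut-offs, offers referral, and adds: "Should safety be a concern, the disclosure provider or study coordinator will schedule additional in-person visits or phone calls as needed". Step 13 repeats none of this.

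**The plan's own figure.** Protocol, Power Calculation: SD 2.2, difference 1.25, 80% power, 50 per group. SAP, Primary Analysis 1.1: two-sided alpha 0.05.
- n = 2 x (1.960 + 0.842)² x (2.2/1.25)² = 48.6, so 49 per group; the t-test version gives 49.6.
- Power at 50 per group is 81.1% (normal) or 80.3% (t).

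The target of 50 per elevated-amyloid group reproduces.

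**How many D- participants are in this position.** Inputs: 370 enrolled and about 10% dropout (Protocol, Power Calculation); 1:1 allocation (Step 7); 25-30% amyloid elevated (SAP, Analysis 1.1 if the planned sample size is not reached; Protocol Section II gives roughly 30%).
- D- randomised: 370/2 = 185. Reaching Visit #7: 185 x 0.9 = 166.5.
- A+D- reaching Visit #7: 185 x 0.25 x 0.9 = 41.6 to 185 x 0.30 x 0.9 = 49.95, so about 42-50.
- Without dropout: 46.25 to 55.5.
- At 30%, A+ completers over both arms are 370 x 0.30 x 0.9 = 99.9, which matches the protocol's 100 completed visits.

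**Share of all who learn of elevated amyloid.** If D+ learn before any dropout and D- after it, the share is 0.9/(1 + 0.9) = 47%. Among completers it is 50/100 = 50%.

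**The case against.** The strongest reply is that D- participants are not left without protection. Section VII item D offers ongoing phone contact as needed, with clinicians ready to respond. Minimizing Risks provides for mental-health referral, and Section IX requires any adverse event to be reported. None of this is limited by arm, and conversation with staff and clinician judgment stand beside the cut-offs throughout. All of this stands. A reader might infer that D- are unprotected after Visit #7, or that GDS and Mini-STAI exceedances could not be observed. The documents do not support either: the scales are unscheduled, not barred, and could be given at an as-needed contact. What remains is that such contact depends on someone noticing distress or the participant reporting it, and the protocol lists scheduled scales as a separate layer (item C against item D).

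D- participants are also better screened before the news. They have mood scales at four visits against two for D+. Their last scores are at most about four weeks old. For D+ the gap from Visit #2 is roughly six weeks: about one month to the scan, then about two weeks after results return. This stands, but screening before the result does not detect a reaction to it.

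The difference between Calls #4 and #5 should not be pressed far. The >25 limit is stated for the IES, not for its intrusion subscale, so Call #4 has no scale with its own numeric limit either. D+ also gets no GDS, mini-STAI or CSSRS at 1-3 days. The larger difference is the two later visits.

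Finally, Minimizing Risks reports that severe or lasting distress has been rare after APOE disclosure. That is relevant, but it concerns genotype. Section I says the likelihood and extent of harm from amyloid results in asymptomatic people had not been carefully assessed.

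**Conclusion.** The point holds as a gap in scheduled detection of distress after the D- scan result, and as an inaccurate safety statement in Section VII. It should be fixed. About 42-50 A+D- participants are concerned (protocol target 50), 47-50% of those told of elevated amyloid. This assumes that the 10% dropout is equal across groups and falls before Visit #7. The count is of people exposed, not people harmed; the documents give no distress rate for amyloid disclosure, so none is projected.

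A reader might go on to infer that the trial's comparisons are compromised. They are not. Delayed disclosure follows the end of data collection, and no randomised comparison, error rate or power figure depends on it. For the same reason, it is no defect that SAP Aim 2 uses the INI-AD only at 6 weeks and 6 months; it leaves out Call #4 scores as well.

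**What to change.** 1. Amend both statements in Protocol Section VII (Psychological risks, and item C). Say that scheduled in-person follow-up with these scales after PET disclosure applies only to D+, and that D- receive one early phone check that would not detect later distress. This costs almost nothing but leaves the gap in place.

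2. In Step 13, at minimum match Step 9: add an IES measure and repeat the cut-off, referral and extra-contact wording. Preferably use the full IES, so that the >25 limit applies, and add the short GDS and mini-STAI, with the CSSRS by investigator judgment. Use the item C limits as triggers: increased monitoring for IES >25, GDS 6-10 or STAI 17-18; referral to the site clinician, in place of exclusion, for GDS >10, STAI ≥19 or serious CSSRS risk. This is more than D+ receive at 1-3 days, because D- have no later scheduled contact. It does not replace later follow-up.

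3. Optionally, tabulate Call #5 scores by amyloid status, as description only.

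The cost of item 2 is a protocol amendment, a new call script and a longer call for about 166 participants, with no new visit or staff. The added content is at least 7 (IES-intrusion) + 15 (GDS) + 6 (mini-STAI) = 28 items, plus the rest of the IES and the CSSRS. Call time is not in the documents; at an assumed 10-20 extra minutes, 166.5 x 10/60 = 27.8 to 166.5 x 20/60 = 55.5 staff-hours over four sites. If the Visit #7 disclosures have already taken place, items 1 and 3 can still be done.

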Analyses of IES as the main secondary outcome and of other measures, will be conducted in a similar fashion. While our main focus for the IES will be upon the contrast between the A+D+ and A-D+ groups, we will also contrast the A+D+ and the D- groups (as long as the A+D- and A-D- exhibit similar outcomes). The D- group may experience increased distress waiting for the disclosure of their imaging, which could reduce our power to explore comparisons between A+D+ and D- groups, although we did not see this occurring in our prior REVEAL studies when participants in the non-disclosure arms were waiting for their genotype data at the end of the study. It will also be of interest to compare the difference between A+D- and A-D- groups, because this comparison would reveal any differences in cognition due to the amyloid burden

itself among participants who do not learn their amyloid status at the fourth visit. We do not expect to find any difference here in only 6 months of follow-up. For Exploratory Aims 1.2 and 2.3, we will examine regression models or MMRM models with interaction terms for race and group to evaluate whether the differences at 6 months between the groups (e.g. A+D+ vs A+D-) are similar for AAs and non-AAs. Point estimates will be considered in addition to confidence intervals and p-values.

For the 6-month follow-up visit digit-span task, we will examine whether working memory performance and pupil dilation responses differ when under high than low threat differentially depending on both disclosure status and amyloid levels.

For the 6-month visit digit-span task, we will examine whether working memory performance and pupil dilation responses differ when under high than low threat differentially depending on both disclosure status and amyloid levels.

Power Calculation

Our objective is to achieve 80% power to detect a difference of moderate effect size (0.4-0.6 SD units) on the primary outcome of ADCS-PACC mean score between the A+D- and A+D+ groups at 6 months.

Assuming a PACC standard deviation of 2.2⁴⁴, 50 individuals per group would provide 80% power to detect a difference of 1.25 PACC units (0.52 SD units) between A+D- and A+D+ at 6 months.

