Primary Analysis 1.1: For this aim we focus on one outcome, ADCS-PACC, and thus use an alpha level of 0.05 to determine statistical significance. First, we will obtain descriptive statistics for those who are in the D+ and D- groups among A+ subjects. Then, we will compare ADCS-PACC scores between D+ and D- groups among A+ subjects using a two-sided test of means. Next, we will compare D+ and D- groups on potential confounders. We will initially consider confounders due to the Covid-19 pandemic (as described below) and then consider other confounders (including age, education, premorbid function, experiences of discrimination). If any are significantly different between the two groups ($p < 0.05$), despite randomization, we will conduct regression analysis adjusting for those confounders that are different. Analyses will be repeated measures (6 wks. and 6 mos.) adjusting for baseline measure at time of randomization. We will focus on 6 month differences, but also check for time-averaged differences between D+ and D- groups. Check ADCS-PACC for normality. If normal, linear regression analysis for repeated measures can be used, specifically a mixed-effects model with repeated measures (MMRM). If not normal, we will use an appropriate transformation to make the distribution more normal. We will also conduct an Intention-to-Treat (ITT) analysis, which will incorporate information from those who drop out over the 6 months, assuming missing at random. This analysis will have better control of type 1 error and power. We will model time as a categorical measure, and the primary outcome will be the estimated difference (contrast) between the two groups (D+ and D-) at 6 months and secondarily the time-averaged difference. We will also apply a model with 3 repeated measures (baseline, 6 wks., 6 months) without adjustment for baseline ADCS-PACC to examine the full trend over time, but this will be a secondary analysis.

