Analysis 1.1 if we do not reach planned sample size: Our plan for this study is to recruit 270 subjects who would be randomized equally to D+ and D- groups. With 10% loss, we expect 120 subjects in each group with about 50% being A+ due to enrichment of *APOE* e4+ participants. Thus, there would be ~60 people in each of the four groups: A+D+, A+D-, A-D+, A-D-. For Aim 1, we powered the study to detect a difference between the A+D+ and A+D- groups. With 60 subjects in each of these two groups, we have 80% power to detect a difference of 1.15 ADCS-PACC points. After pursuing this plan for several years we found that the expected 50% split between A+ and A- participants was too optimistic and in fact we found that the proportion of A+ subjects enrolled in the study was hovering between 25% and 30%, thereby reducing the numbers available for evaluation of Aim 1, the primary research question for the study. In June, 2018, we applied for a supplement to this research project to aid us in attaining needed sample size for Aim 1. We revised our estimated sample size needed for Aim 1 to be 50 in each group (A+D+, A+D-), determining that we could detect a moderate meaningful difference of 1.2451. If we are not able to attain the sample size that we expect (~50 in each group), we will conduct an analysis of the existing sample. If the result is significant, we then had more power than we thought we might; that is, the difference between the two groups was greater than 1.2451. If the difference between the two groups is not significant, we will examine the confidence interval for the difference to obtain a range of estimates of possible differences, given our sample size.

Outliers: Components of the ADCS-PACC and the overall score will be examined for outliers. We will exclude values that are more than 2 standard deviations from expected mean values (based on the literature). In addition, we will consult visit notes and TOMM scores to see if anything unusual might be a factor in the outliers.

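### With SD 2.2, 50 per group gives 80% power from about 0.57 SD, not the printed 0.52, so this calculation does not cover the lower part of the 0.4-0.6 SD target

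*Protocol*

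**What the plan says.** Protocol section VI, Power Calculation, gives the aim: "Our objective is to achieve 80% power to detect a difference of moderate effect size (0.4-0.6 SD units) on the primary outcome" (the sentence goes on to name the 6-month ADCS-PACC contrast between A+D- and A+D+). The next sentence assumes a PACC standard deviation of 2.2 and states: "50 individuals per group would provide 80% power to detect a difference of 1.25 PACC units (0.52 SD units". The target of 50 per elevated-amyloid group is then said to rest on this calculation.

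The SAP, under the heading for Analysis 1.1 if the planned sample size is not reached, reports the superseded plan: "With 60 subjects in each of these two groups, we have 80% power to detect a difference of 1.15 ADCS-PACC points". For the revised 50 per group it speaks of "determining that we could detect a moderate meaningful difference of 1.2451". It adds that if the result is significant, the group difference was larger than 1.2451. If it is not significant, the confidence interval will be examined.

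SAP Primary Analysis 1.1 will "use an alpha level of 0.05 to determine statistical significance". It begins with a two-sided comparison of means and then specifies: "Analyses will be repeated measures (6 wks. and 6 mos.) adjusting for baseline measure at time of randomization". The protocol's Data Analysis section instead makes a mixed model on three repeated measures primary, with baseline as a covariate in an additional model. Neither document names the test behind the power figure, says whether 2.2 is a raw or residual SD, or gives a correlation between baseline and 6-month PACC.

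**The concern.** The calculation follows directly on an objective of 0.4-0.6 SD, and its detectable effect is labelled 0.52 SD, close to the middle of that band. A reader would conclude that 50 per group has 80% power for a mid-range effect and something not far below it at the lower end.

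This is the trial's primary question: whether disclosure biases the cognitive outcome used in prevention trials. If the comparison is null, the power statement decides how much reassurance readers take from it. If the result is significant, the SAP's use of 1.2451 as a floor would lead to an overstated effect.

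**Working it through.** **Inputs.** SD 2.2, 50 per group and 1.25 units (protocol, Power Calculation); 1.2451 and the 60-per-group figure of 1.15 (SAP, Analysis 1.1 if the planned sample size is not reached); two-sided test, alpha 0.05 (SAP, Primary Analysis 1.1); 1:1 allocation (protocol, Step 7). The 50 per group are completed 6-month visits, so dropout has already been allowed for.

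**Step 1: reproduce the plan's figure.** For an unadjusted two-sample t-test with n = 50 per group (98 degrees of freedom), the standardised difference giving 80% power is 0.5659. In PACC units this is 0.5659 × 2.2 = 1.245, which agrees with the SAP's 1.2451. The normal approximation gives 1.233 and a one-sided test 1.102, so neither matches. Power at exactly 1.25 units is 80.3%. The test is inferred from this match; the documents do not state it.

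**Step 2: check the label.** 1.25 / 2.2 = 0.568 and 1.2451 / 2.2 = 0.566. Neither is 0.52. The superseded figure gives 1.15 / 2.2 = 0.523, so the label may have been carried over from the 60-per-group calculation. That origin is a guess; the mismatch is not.

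**Step 3: power across the stated range.** Same t-test, n = 50, noncentrality = d × √(n/2) = 5d:

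| Effect (SD units) | PACC units (× 2.2) | Power | n per group for 80% |
|---|---|---|---|
| 0.40 | 0.88 | 51% | 100 |
| 0.50 | 1.10 | 70% | 64 |
| 0.52 | 1.14 | 73% | 60 |
| 0.568 | 1.25 | 80% | 50 |
| 0.60 | 1.32 | 84% | 45 |

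**Step 4: what significance implies.** The smallest observed difference with p < 0.05 is t × SD × √(2/n). At 50 per group it is 1.984 × 2.2 × 0.2 = 0.87 points. The SAP passage concerns a shortfall, which raises the threshold: at 45 per group it is 1.987 × 2.2 × √(2/45) = 0.92. It reaches 1.2451 only at about 25 per group (2.011 × 2.2 × √(2/25) = 1.25). Even there, the threshold applies to the observed difference, not the true one.

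**Step 5: effect of baseline adjustment (assumed inputs).** If 2.2 is a raw SD and baseline correlates r with 6-month PACC, the residual SD is 2.2 × √(1 - r²), and the detectable difference is 1.245 × √(1 - r²):

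| r (assumed) | Detectable, points | Detectable, SD units | Power at 0.4 SD | Power at 0.5 SD |
|---|---|---|---|---|
| 0 | 1.245 | 0.57 | 51% | 70% |
| 0.5 | 1.08 | 0.49 | 63% | 82% |
| 0.7 | 0.89 | 0.40 | 79% | 93% |
| 0.8 | 0.75 | 0.34 | 91% | 98% |

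Under these assumptions, 80% power at 0.4 SD needs r of about 0.71, and at 0.5 SD about 0.47.

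**The case against.** The strongest reply is that the protocol gives 0.4-0.6 SD as an objective, and the bracket can be read as defining a moderate effect. Achieved power is claimed at one point only, 1.25 units. That claim reproduces and, at 0.57 SD, lies inside the band. This stands. A reader might infer that the protocol promises 80% power at every effect from 0.4 to 0.6 SD, but the text does not say so.

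A second reply is that sizing on an unadjusted comparison is ordinary and usually conservative. The SAP's repeated-measures model adjusts for baseline, so 51% and 70% may understate its power. This also stands, if 2.2 is a raw SD. It rules out another tempting reading, that the calculation is wrong because it does not match a baseline-adjusted primary analysis. That description fits only the SAP's repeated-measures step. The SAP's first step is a plain test of means, and the protocol's primary model treats baseline as one of three outcomes.

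A third reply is that the SAP already turns to the confidence interval when the result is not significant, which limits the risk of over-reading a null. That is sound, though it is written only for a sample-size shortfall.

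None of these replies rescues the 0.52 label or the inference drawn from significance.

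**Conclusion.** The point holds in a limited form. The power claim for 1.25 units is right; its expression as 0.52 SD is wrong and should be 0.57. At the printed 0.52 SD the calculation delivers about 73%, not 80%. It reaches 80% only near the top of the target band, with 70% at 0.5 SD and 51% at 0.4, and neither document says so. These figures rest on SD 2.2, two-sided alpha 0.05, 50 completers per group and an unadjusted t-test.

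The documents do not settle whether the planned models do better. That depends on which model is primary, what kind of SD 2.2 is, and a baseline correlation that is not given. The adjusted figures above are therefore illustrations, not evidence that the objective is met or missed.

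The SAP's statement that significance implies a difference above 1.2451 is a separate error. It confuses the difference detectable with 80% power with the threshold for significance, about 0.87 points at 50 per group.

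**What to change.** - **Protocol, Power Calculation.** Restate as: 50 per group gives 80% power for 1.25 points (0.57 SD) by an unadjusted two-sided t-test; power is 70% at 0.5 SD and 51% at 0.4 SD. The lower part of the range is then not presented as covered by this calculation.
- **SAP, Analysis 1.1 if the planned sample size is not reached.** Identify 1.2451 as the unadjusted difference detectable with 80% power at 50 per group. Delete the inference that a significant result means the difference exceeded it. Labelling the figure as unadjusted would not repair that inference by itself.
- **Optional.** State whether 2.2 is a raw SD. If it is, add that the SAP's baseline-adjusted model would have more power, with detectable differences of 1.08, 0.89 and 0.75 points at assumed correlations of 0.5, 0.7 and 0.8.

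The cost is a few sentences, and one printed figure becomes less favourable. Enrolment and the planned analyses do not change.
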